## GLOSSARY OF DEFINITIONS AND TERMS

Obstructive Sleep Apnea: Obstructive sleep apnea (OSA) is a disorder in which a person frequently stops breathing during his or her sleep. It results from an obstruction of the upper airway during sleep that occurs because of inadequate motor tone of the tongue and/or airway dilator muscles.

Positional Obstructive Sleep Apnea (POSA): Defined as a total apnea-hypopnea index (AHI) > or = 5 with a 50% reduction in the AHI between the supine and non supine postures, and an AHI that normalizes (AHI <5) in the non-supine position.

Apnea: Cessation of breathing for 10 seconds or more

Hypopnea: A decrease in airflow associated with subsequent desaturation

Head Pitch: The movement of the head as determined by chin position, up or down

Head Roll: The movement of the head as determined by head rotation from right to left or left to right.

Independent of Torso position: In the context of this protocol, "Independent of Torso position" means sleeping supine while maneuvering the head from left to right or right to left to potentially alleviate collapse of the upper airway.

Polysomnogram: The overnight measurement of 6 or more physiological variables that includes a minimum number of EEG measurements, cardio-respiratory data, EKG data and data pertaining to movement during the sleep period.

Montages: Refers to a specific sequences of collection of physiological data in a sleep study (polysomnogram). The montage specifically details how and what electrodes are placed on the patient.

Participant Clinical Data (PCD): Individual assignable bonded clinical forms that contain research data pertaining to overnight sleep study and screening data. PCD shall only contain the assigned study number with no identifying information and is the property of the Sponsor.

AHI (Apnea-Hypopnea Index): The number of abnormal respiratory events (including cessation of breathing of decreased airflow) divided by the Total Sleep Time (TST). The final number is used to diagnose and determine the severity of patient symptoms.

[figure not shown]
## The Effect of Head Pitch and Roll Rotation Independent of Torso Position on the AHI in Positional Obstructive Sleep Apnea

## 1. Background and Study Aim

The prevalence of Obstructive Sleep Apnea (OSA) can be as high as 9% within the general population. A subset of OSA, described as Positional Obstructive Sleep Apnea (POSA), defined operationally as apneas occurring during specific positions while asleep, occurs predominantly in the supine position. Approximately 30% of obstructive sleep apnea (OSA) patients have supine-predominant OSA.(2) The patients diagnosed with obstructive sleep apnea that position dependent are at least twice as severe when sleeping supine. In one study, the prevalence of POSA was as high as 50% in patients diagnosed with mild sleep apnea (AHI, 5-15/h) and as low as 7% in patients diagnosed with severe sleep apnea (AHI > 30/hr) (1). Results from another study of 1170 adults Asian patients conducted over a span of four years, from 2004 through 2008, demonstrated that the presence of POSA is almost three-fourths of the patients and that the AHI is the most dominant factor for determining positional dependency, followed by BMI. (3)

It has been hypothesized that POSA may also occur independent of torso position but is affected solely by head position, independent of supine. A review of drug-induced endoscopy in OSA which is predominantly performed in the supine position concluded that head rotation improves upper airway collapse during this procedure in supine position. (4). Thus while the treatment of POSA has generally been directed at limiting sleeping in the supine position without regards to effects of head position, rotating the head away from the 90 degree position might alleviate the "crush force" seeking to close the upper airway. This study seeks to verify whether rotation of the head while sleeping in the supine position during polysomnography affects the calculated AHI. Head rotation will be defined in terms of degree rotation from a 90 degree starting position (head position aligned with supine position) and rotating the head from right to left defining the movement in terms of a widening angle from 0 degrees to 90 degrees through 180 degrees, thus reducing the AHI. A secondary aim is to develop an algorithm that can predict whether a specific degree of head rotation can be assigned to a percentage reduction in AHI.

The diagram below, provided by the sponsor, illustrates this maneuver:

[figure not shown]
## 2. Study Design

This is a non-randomized study with the intent of enrolling up to 10 participants to collect up to ten completed polysomnograms. The polysomnogram montages have specifically been altered to include the investigational channels for head pitch and roll. Head pitch and roll recorded data have been added with recorded data tagged as degrees of change from the vertical (head aligned with supine torso) as 90 degrees. Eligible participants, those meeting the inclusion criteria, will provide written informed consent. We will recruit stable, previously diagnosed POSA patients who self-report persistent apnea and who are currently on treatment by PAP.

Eligible participants will come into the Sleep Center for a screening visit. Following the screening visit, qualified participants will be asked to complete one overnight sleep study (polysomnogram) monitored by staff technologists. The sensor patch will be placed on the forehead as illustrated below and calibrated along with other calibrations that are required to complete a standard polysomnogram.

POSA will be determined as per standard collection procedures and when the threshold AHI is calculated, the research technologist shall initiate the head roll from right to left at specific degree changes to eliminate apneas and hypopneas. The changes in head roll shall be accomplished by the placement of pillow wedges to keep the head stable at the particular degree settings. The pillow wedges are selected for the predetermined angle of roll. Additionally, during these maneuvers, the torso shall be maintained in the supine position for a

specific amount of time to assess the effects of head roll independent of torso position in addition to sleeping positions that are comfortable for the participant. The data will be recorded and analyzed as such utilizing standard polysomnography body position sensors.

(Illustration of head pitch and neck roll sensor)

Following collection of overnight data, data will be scored as per standard polysomnography scoring including specific scoring of head pitch and roll in correlation with other polysomnographic data. The sleep study will be reviewed by the principle investigator to determine whether the maneuvering of head pitch and roll had normalized the AHI (See Appendix A).

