## Study Procedures:

- Subject (participant) how are eligible will be scheduled for a daytime screening session at the Sleep Center located at [name] with either the Study Coordinator or Staff Research Technologist. Following the screening visit and signed consent, qualified participants shall be asked to complete an overnight sleep study (polysomnogram).
- Following the screening visit, participant will be scheduled for an overnight sleep study and participant will arrive at scheduled time, generally between the hours of 7:00 PM and 8:30 PM.
- Research Technologist greets patient, verified individual personal information and matches the assigned Participant Clinical Data Binder (PCD) including the assigned study number.
- 4. Research Technologist shall complete the demographic section of the PCD and explain the sleep study to the participant.
- 5. Research Technologist shall attach electrodes as per Sleep Systems Research Montage and escort participant to assigned sleep room and will further explain to the participant the "process" of gathering sleep study data (i.e. calibrations, use of call button and the system that will be utilized to rotate the head as per protocol.)

- Research Technologist will attach forehead sensor to the most level surface of forehead without getting too close to the eyes with medical tape. Small foam wedges may be necessary under the sensor to adjust for calibration. Research Technologist will confirm the pitch and roll angles to be 90 degrees +/- 5 degrees.
- 7. Participant is allowed to watch Television or read until "Lights Out" as determined by the Research Technologist.
- 8. Once recording has commenced the Research Technologist shall complete the scoring forms as per protocol. Once the baseline AHI for POSA is verified (generally about 2 hours following sleep) Research Technologist shall enter the Sleep room and initiate neck roll maneuvers, utilizing wedge pillows as follows:
  - a) 30 degrees on right for 45 minutes.
  - b) 60 degrees on right for 45 minutes
  - c) 90 degree (head and neck aligned with supine torso) for 45 minutes
  - d) 120 degrees to left for 45 minutes
  - e) 150 degree to left for 45 minutes.

The goal is to normalize AHI (<5).

9. If no calculated AHI indicative of POSA (>5) is achieved the participant will be awakened at 7:00 AM and discharged from Sleep Center.

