#### APPENDIX A

# **Sleep Study Score Sheet**

This score sheet represents the ideal baseline information that Sleep Systems would like to see for the sleep study. All numbers in the table should be replaced with actual values

Measured Head Pitch	Measured Head Roll	Pillow Angle (°) or Style	Torso Position	Start Time	Stop Time	Measured Duration	Measured AHI Events	Meası Oxyg Satura
Angle(°)	Angle(°)	Used				(Min.)	/Hour	(%
70-90	90	Flat	Supine	10:00P	11:00P	60	25	90
70-90	90	Flat+Towell	Side	11:00P	12:00P	60	25	90
70-90	15 or 165	15	Side	12:00A	1:00A	60	5	100
70-90	15 or 165	15+Towell	Supine	1:00A	2:00A	60	5	100
70-90	0 or 180	Flat	Side	2:00A	3:00A	60	17.5	96
70-90	45 or 135	45	Side or Supine	2:00A	3:00A	60	17.5	96

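### Head roll is measured from the vertical, but torso angle need not be logged nor supine verified within a limit, so independence from torso position is not secured

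*Protocol*

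**What the plan says.** The title and section 1 of the Protocol ask whether turning the head during supine sleep changes the AHI. A secondary aim is an algorithm linking degree of rotation to percentage reduction in AHI. The Glossary explains independence from torso position as sleeping supine while the head is turned, and gives no angular limit for supine.

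**Head.** Section 2 states: "The sensor patch will be placed on the forehead as illustrated below". Roll is recorded in degrees, "tagged as degrees of change from the vertical (head aligned with supine torso) as 90 degrees". At set-up (Study Procedures) there is a numerical check: "Research Technologist will confirm the pitch and roll angles to be 90 degrees +/- 5 degrees".

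**Torso.** Section 2 says that "during these maneuvers, the torso shall be maintained in the supine position for a" length of time that is not given, and the same sentence goes on "in addition to sleeping positions that are comfortable for the participant". The data are to be recorded and analysed "utilizing standard polysomnography body position sensors". The output type and resolution of these sensors are not stated.

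**Where the results are written down.** Section 2 points to Appendix A in connection with judging whether AHI normalised. Its score sheet has head pitch and head roll in degrees, but the "Torso Position" column holds words: Supine, Side and, on the 45/135 row, Side or Supine. The Apnea Severity Calculator takes peak AHI, head pitch and head roll, and nothing about the torso.

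**The concern.** A head angle taken from the vertical contains any roll of the trunk beneath it. If the trunk turns part of the way after the head and is still classed Supine, the score sheet row looks the same as one with the trunk flat.

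This matters because of who is enrolled. The Glossary defines positional apnea partly by "an AHI that normalizes (AHI <5) in the non-supine position", so participants are selected for an AHI that responds to trunk position. If partial roll also lowers the AHI, and if the trunk follows further at the larger wedge angles, a relation between head angle and AHI could appear with little or no head effect. The error would favour the hypothesis and would enter the angle-to-AHI algorithm. The Data Analysis section says the results may be used to power a larger trial, so it could carry forward.

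**Working it through.** The Protocol gives no figure on this point to reproduce. The check is geometric, followed by a reading of which records could reveal trunk roll.

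**1. Identity.** For rolls in the same direction, H = T + N, where H is head roll off the vertical, T is trunk roll and N is head rotation relative to the trunk. H equals N only when T = 0.

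**2. Inputs.** The wedge settings in Study Procedures, step 8, are 30, 60, 90, 120 and 150 degrees. Taking |setting − 90| gives H = 60, 30, 0, 30 and 60 degrees. The values of T below are assumptions, because the Protocol gives no boundary between Supine and Side.

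**3. Results.** The trunk's share of the recorded roll is T/H, and N = H − T.

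| Assumed T | H = 30 (settings 60, 120) | H = 60 (settings 30, 150) |
|---|---|---|
| 0 | 0%, N = 30 | 0%, N = 60 |
| 5 | 5/30 = 17%, N = 25 | 5/60 = 8%, N = 55 |
| 15 | 15/30 = 50%, N = 15 | 15/60 = 25%, N = 45 |
| 30 | 30/30 = 100%, N = 0 | 30/60 = 50%, N = 30 |
| 45 | trunk beyond head | 45/60 = 75%, N = 15 |

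**4. Which record would show T?**
- The head sensor need not. The wedges hold the head at its setting, so H can stay constant while T changes.
- The score sheet shows only a change of category. Its illustrative rows list the head reading 15 or 165 once with Side and once with Supine, so the head reading does not identify the torso position. The 45/135 row does not separate the two at all.
- The calculator has no torso input, so any trunk effect would be absorbed into the roll angle.
- The body position channel may show T, depending on its output. The Protocol does not describe that output or require an angle to be taken from it.

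**5. From angle to AHI.** With no head effect, the spurious fractional fall in AHI within a block is f × g, where f is the share of block sleep with the trunk part-rolled and g is the share of events that this removes. The Protocol gives neither. The Glossary describes AHI off supine, not AHI during partial roll inside the Supine class. The product could lie anywhere from 0 upwards, so no size can be derived.

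**The case against.** The strongest reply is that the Protocol already handles the torso. It asks for the trunk to be kept supine during the manoeuvres, technologists monitor the night, and body position sensors record. The score sheet is a summary form with placeholder numbers, and the research montage is not shown. The Glossary defines independence as sleeping supine with the head turned, which the plan roughly delivers. Epoch filters and sensitivity analyses can sit in a statistical analysis plan.

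Much of this stands, and it rules out several stronger readings:
- A reader might infer that partial trunk roll would go unseen. The document does not show that. A full turn to the side would be seen, and whether a partial roll is seen depends on a resolution that is not stated.
- A reader might infer that no result could be called independent of torso position. That is too absolute, given the instruction to keep the torso supine and the Glossary's own definition.
- A reader might take trunk roll to be the leading rival explanation. It is a plausible one. The openly admitted comfortable positions and the pooled row are others, and nothing ranks them.
- A reader might size the bias against the sheet's 45/135 row, where AHI falls from 25 to 17.5 (7.5/25 = 30%), since for example f = 0.6 and g = 0.5 give 0.6 × 0.5 = 30%. Those inputs have no source. The row is a placeholder coded Side or Supine, and 45/135 is not a wedge setting in Study Procedures.
- A reader might conclude that head minus torso roll should replace the exposure. Section 1 defines rotation from the 90 degree position and describes a force closing the airway, which can be read as an angle to gravity. A vertical reference suits that hypothesis.

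What the reply does not meet is data capture. There is no limit for supine and no requirement to log torso angle, and the sentence asking for a supine torso also admits other positions. Each participant has one study night, and an angle not stored that night cannot be supplied by a later analysis plan.

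**Conclusion.** The point holds as a gap in what the plan secures. Head roll is an angle from the vertical, torso is written down by category, and supine is not verified within any stated limit. Trunk roll inside the Supine class would therefore be credited to the head.

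The geometric shares (17% to 100% of a 30 degree roll, 8% to 75% of a 60 degree roll) depend wholly on assumed trunk rolls of 5 to 30 and 5 to 45 degrees respectively. They describe the angle, not the AHI. The size of any AHI bias cannot be computed from the document. Its direction, in favour of the hypothesis, assumes that the trunk sometimes follows the head and that partial roll lowers AHI in these participants. No sample size or error rate is affected, since none is stated. This is a worthwhile, inexpensive improvement and does not invalidate the study.

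**What to change.** - Add a Measured Torso Roll Angle column to the Appendix A score sheet, read from the body position channel already recorded.
- Give Side and Supine separate rows, and do not pool them for any head angle.
- State before the first recording a tolerance within which the torso counts as supine. Base the head-roll conclusion and the angle-to-AHI algorithm on sleep epochs that meet it, and repeat with a wider tolerance as a sensitivity analysis. The Protocol gives no basis for a particular value, so the sponsor should choose and justify it.
- Keep head roll from the vertical as the exposure. Report head minus torso roll only as a supplementary description.
- If the channel stores categories only, word the conclusion as head roll with the torso classed supine.

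The cost is one extra column and an epoch filter. Some minutes will drop out of the 45-minute blocks, and the claim may become narrower than the title.

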# Apnea Severity Calculator

## STEP 1

Enter the subjects peak measured AHI in the yellow box below, at a head pitch and roll angle near 90 degrees

Measured Peak

AHI (events/hour)

25

## STEP 2

Enter the pitch and roll angle in the yellow boxes below to see the calculated AHI index in green

Measured	Measured	Calculated AHI		
Head	Head			
Pitch Angle (°)	Roll Angle (°)	(events/Hour)		
90	90	25.0		

- 1)HAVE YOU BEEN TOLD THAT YOUR SLEEP APNEA IS POSITIONAL (IT HAPPENS MOSTLY WHEN YOU SLEEP ON YOUR BACK)?
- 2)HAVE YOU HAD A SLEEP STUDY WITHIN THE PAST 2 YEARS?
- 3)ARE YOU NOW ON CPAP THERAPY?
- 4) ARE YOU BETWEEN THE AGES OF 21 AND 60 YEARS?

IF YOU ANSWERED YES TO THE ABOVE,
YOU MIGHT BE ELIGIBLE AND
COMPENSATED TO PARTICIPATE IN A
CLINICAL TRIAL. ASK YOUR PHYSICIAN
FOR MORE DETAILS

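### Head roll is not separated from head support: wedges are chosen by roll angle alone, the support at the 90-degree reference is not stated, and pitch is recorded but not held constant across blocks

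*Protocol*

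**What the plan says.** Section 1 of the protocol states the aim as the effect of head rotation on AHI during supine sleep. A secondary aim is an algorithm linking degree of rotation to percentage reduction in AHI.

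Section 2 describes how roll is produced: "The changes in head roll shall be accomplished by the placement of pillow wedges to keep the head stable at the particular degree settings". It adds: "The pillow wedges are selected for the predetermined angle of roll". On measurement it says: "The polysomnogram montages have specifically been altered to include the investigational channels for head pitch and roll".

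Study Procedures step 6 sets the only pitch tolerance, at sensor placement: "Research Technologist will confirm the pitch and roll angles to be 90 degrees +/- 5 degrees". Step 8 follows a baseline of about two hours with five blocks of 45 minutes, at 30, 60, 90, 120 and 150 degrees. The list is introduced as a wedge-pillow procedure. The support used in the 90-degree block (8c) or during baseline is not given.

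The score sheet in Appendix A begins with the row "70-90 90 Flat Supine" and gives pitch as 70-90 in all six rows. It also says: "All numbers in the table should be replaced with actual values".

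The Apnea Severity Calculator asks for the peak AHI at pitch and roll near 90, and then: "Enter the pitch and roll angle in the yellow boxes below".

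**The concern.** If each roll angle comes with its own support, a difference in AHI between the 90-degree reference and a rotated block reflects the angle and the support together. A wedge or towel may raise the head or move the chin as well as turn the head. Each participant has one night and one block per angle, so no angle is planned on two different supports.

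Pitch adds a related risk. The sponsor's calculator treats pitch as a predictor of AHI and places the peak near 90 degrees. A support that moved the chin away from 90 in the rotated blocks would then lower AHI in the direction the roll hypothesis predicts. An algorithm for roll built on such data would absorb that effect, as would any larger trial powered from this pilot.

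**Working it through.** No sample-size or power figure bears on this point, so the check sets the passages side by side.

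**1. Score sheet rows (Appendix A; AHI values are the sheet's own examples)**

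| Row | Roll | Pillow | Torso | AHI |
|---|---|---|---|---|
| 1 | 90 | Flat | Supine | 25 |
| 2 | 90 | Flat+Towell | Side | 25 |
| 3 | 15 or 165 | 15 | Side | 5 |
| 4 | 15 or 165 | 15+Towell | Supine | 5 |
| 5 | 0 or 180 | Flat | Side | 17.5 |
| 6 | 45 or 135 | 45 | Side or Supine | 17.5 |

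Six rows give 6 × 5 / 2 = 15 pairs. Two pairs share the same roll (1 and 2; 3 and 4), which leaves 15 − 2 = 13 pairs that differ in roll.

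- Same pillow: 1 of 13 (rows 1 and 5), and there the torso differs (supine against side).
- Same pillow and compatible torso: 0 of 13.
- Same listed pitch range: 13 of 13.

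The supine contrast between rows 1 and 4, from 25 to 5, changes roll, wedge and towel together. The contrast between row 1 and row 6 taken as supine, from 25 to 17.5, changes roll and wedge.

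**2. The blocks in step 8**

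Distances from 90 degrees are 60, 30, 0, 30 and 60, over 5 × 45 = 225 minutes. Assume one support per distance, mirrored left and right. The support categories then coincide exactly with the three roll distances (0, 30, 60), and a model with both factors can estimate only one of them. The repeats on left and right repeat the same pairing, so they do not help. Comparing 30 with 60 degrees off centre would be free of a support effect only if both wedges held the head alike, which the protocol does not require.

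**3. Pitch**

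- Set-up check: 90 ± 5, that is 85 to 95, a span of 10 degrees.
- Score sheet entry: 70 to 90, a span of 90 − 70 = 20 degrees.
- Overlap: 85 to 90.

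The first is a calibration tolerance. The second stands among example readings. Their mismatch shows that the status of 70-90 is unclear; it does not measure a shift in pitch.

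**4. Size**

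Wedge heights are not given and the calculator formula is not shown (only that 90/90 returns the entered peak, 25.0). An effect in AHI units cannot be derived.

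**The case against.** The strongest reply is that the flat-pillow and towel evidence comes only from an example sheet whose numbers are to be overwritten. Its rotated angles (0/180, 15/165, 45/135) are not those of step 8 (30, 60, 120, 150). The sheet is also not a clean split: it has a towel at 90 degrees and a flat pillow at 0/180, both with the torso on the side. All of this stands. A reader might infer that block 8c is run on a flat pillow, but step 8 lists it under the wedge procedure and leaves its support open.

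A reader might also infer that pitch changes along with roll. The documents do not show it: the sheet lists the same range in every row. Nor is pitch beyond later analysis. It is a recorded channel with an entry per segment, and how to adjust for it could be left to an analysis plan. Likewise 70-90 is nowhere stated as an acceptance limit, so it does not plainly contradict the set-up tolerance.

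Finally, the study title and the investigator's review cover pitch as well as roll, so forcing pitch to one value would remove variation that a two-input calculator needs. That is a good reason to account for pitch rather than only to fix it.

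What these replies do not answer is the tie between support and roll. Logging the pillow style does not separate two things that move together. An analysis plan cannot supply a comparison the procedure never makes.

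**Conclusion.** The point holds in a limited form. Wedges are selected by roll angle, no text asks for equal support, the support at baseline and in 8c is unstated, and the sponsor's own example layout contains no contrast in roll at fixed pillow and torso (0 of 13 pairs). Pitch is measured but not controlled after set-up, which is a risk and not a demonstrated shift.

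To say that no fall in AHI could be credited to roll would go too far. The neutral support may already be intended in 8c, and the size of any support effect is unknown. The conclusion assumes that each roll distance has its own wedge and that wedges can differ from the reference support in head height. The direction of a possible pitch bias rests on the calculator placing the peak near 90. This is an inexpensive improvement to a pilot of up to 10 participants; it does not invalidate the design.

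**What to change.** 1. In step 8, state the support used at baseline and in 8c. For 8c use a neutral (zero-roll) support of the same type as the wedges and as close to them in head height as is feasible. Use a towel in all five blocks or in none.
2. Take the participant's supine pitch at 90 degrees roll during baseline, before 8a, as the reference. Block 8c comes third, so its own pitch is not available when 8a and 8b begin. Read pitch from the sensor already worn at the start of each block.
3. Make the roll comparison on supine segments and account for recorded pitch, either by restricting to segments near the baseline pitch or by showing pitch per block with a sensitivity analysis.
4. In Appendix A, say whether 70-90 is an example or a limit, and reconcile it with the 90 ± 5 of step 6.

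The cost is one neutral pillow, one reading per block (five per night), and some minutes lost if the comparison is restricted by pitch. How many minutes cannot be told from the documents; the sensitivity analysis avoids that loss.

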## Data Analysis, Safety, Confidentiality and Compensation:

Demographic data will be presented with descriptive analysis. Sleep Study data will be scored as per AASM (American Academy of Sleep Medicine) standards and will be tested for normal distribution with respect to prediction of neck and head roll angles normalizing the AHI (Apnea Hypopnea Index). Normalizing AHI or reducing to sufficient levels to decrease the symptoms of untreated POSA will be documented for each subject. The results of this pilot study may be used to power a larger trial.

With respect to confidentiality, a unique identification number designed to protect the identity of participant will be used to identify the participant on report forms, recruitment logs, data forms or other report containing information. Each participant will sign a HIPAA authorization

permitting the release of protected health information to the sponsor, the investigative team, and regulatory authorities.

Safety maintenance at the Sleep Center during the overnight visit shall be maintained in accordance Policies and Procedures currently in place at the Sleep Center located at [name].

Participants will be compensated for travel expenses and time commitment. Participants will be compensated \$50.00 for the screening visit and up to \$400.00 for each overnight sleep study they complete.

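### The head-roll question is about supine sleep, but the score sheet admits side-lying rows, the calculator has no torso input, and only a vague line separates the two

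*Protocol*

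**What the plan says.** **The question.** The Protocol's Glossary defines independence from torso position as lying supine while the head is turned. Section 1 states the aim as the effect of head rotation on AHI during supine sleep. Its secondary aim is an algorithm linking a degree of rotation to a percentage reduction in AHI.

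**The conduct.** Section 2 keeps the torso supine during the manoeuvres for a set but unstated time, to assess head roll "independent of torso position in addition to sleeping positions that are comfortable for the participant". It continues: "The data will be recorded and analyzed as such utilizing standard polysomnography body position sensors". Head data are "tagged as degrees of change from the vertical (head aligned with supine torso) as 90 degrees", so the reference for roll is the vertical and not the participant's torso.

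**The manoeuvres.** Study Procedures, step 8, lists five angles of 45 minutes each (30, 60, 90, 120 and 150 degrees). Only one item names the torso: "90 degree (head and neck aligned with supine torso) for 45 minutes". The stated goal, an AHI below 5, has no torso condition.

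**The tools.** For the judgement that AHI has normalized, Section 2 refers to Appendix A. That sheet has a torso column, with three rows marked Side, two Supine and one "Side or Supine". The Apnea Severity Calculator takes a peak AHI and then instructs: "Enter the pitch and roll angle in the yellow boxes below to see the calculated AHI index in green". It has no torso field.

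**The analysis.** The Data Analysis section speaks of "prediction of neck and head roll angles normalizing the AHI" and names no torso position.

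**The concern.** The Glossary defines positional apnea by a non-supine AHI below 5. In these patients torso position is therefore a strong determinant of AHI, and it is the factor that the head-roll question has to hold fixed.

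Side-lying time can be credited to head roll in two ways. If a row is summarised by manoeuvre step, any side-lying time in it lowers the AHI attributed to that step. If data are sorted by measured roll, a participant who turns the whole body with the head in line also records a roll away from 90 degrees, because roll is referenced to the vertical. Either way, a torso effect can look like a head effect.

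The secondary aim is the most exposed. An algorithm trained on pitch, roll and AHI, without torso position, would absorb the torso effect into the roll coefficient. The Protocol says that the results may be used to power a larger trial, so an inflated effect could carry forward.

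**Working it through.** The Protocol gives no calculation on this point, so there is no figure to reproduce. The check has two parts.

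**1. Score sheet rows by torso position (Appendix A, template rows of 60 minutes)**

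| Torso | Rows | Minutes | Roll angles |
|---|---|---|---|
| Supine | 2 | 120 | 90; 15 or 165 |
| Side | 3 | 180 | 90; 15 or 165; 0 or 180 |
| Either | 1 | 60 | 45 or 135 |
| Total | 6 | 360 | |

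Only two of the four roll settings on the form have a clearly supine row. The numbers on the form are placeholders. The layout is what matters here.

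**2. Size of a false reduction if head roll has no effect**

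Inputs:
- S, supine AHI: 25 (the template's value at roll 90), and 10 as an assumed milder case.
- n, non-supine AHI: 2 assumed, with 0 to 4.9 as the range allowed by the Glossary definition.
- s, side-lying share of sleep in the segment: 20% to 50% assumed. The Protocol gives no bound.

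Formulas: segment AHI = S(1 − s) + n·s, and false reduction = s(1 − n/S).

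| S | n | s | Segment AHI | False reduction |
|---|---|---|---|---|
| 25 | 2 | 20% | 25×0.8 + 2×0.2 = 20.4 | 18.4% |
| 25 | 2 | 50% | 25×0.5 + 2×0.5 = 13.5 | 46.0% |
| 25 | 0 | 20% / 50% | 20.0 / 12.5 | 20.0% / 50.0% |
| 25 | 4.9 | 20% / 50% | 20.98 / 14.95 | 16.1% / 40.2% |
| 10 | 2 | 20% / 50% | 8.4 / 6.0 | 16.0% / 40.0% |

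**False AHI below 5 in a mixed segment.** This needs S(1 − s) + n·s < 5, that is s > (S − 5)/(S − n). With n = 2:
- S = 25: 20/23 = 87.0%
- S = 15 (assumed): 10/13 = 76.9%
- S = 10: 5/8 = 62.5%

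The required share exceeds one half whenever S > 10 − n, here S > 8. For supine AHI of 8 or less, half the segment or less would be enough.

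**The case against.** The strongest reply is that the Protocol already separates the two effects. The full sentence in Section 2 gives the supine hold the purpose of assessing head roll, and the next sentence says that data are analysed with body position sensors. Every row of the form has a torso column and start and stop times, so side-lying data are labelled. The combined entry sits beside paired angles such as 45 or 135 and probably marks alternatives to be filled in. Section 1 also raises the hypothesis that apnea may depend on head position alone, so collecting side-lying data is legitimate. A detailed rule on which sleep counts could sit in an SAP that is not shown.

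Much of this stands. The data needed to separate head from torso are recorded, and collecting side-lying sleep is no fault. But the sensor sentence does not say which data answer the head-roll question. An SAP rule would also leave unchanged the mismatch between the supine-only aim and a form and calculator that this Protocol itself lays out.

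A reader might infer more than the documents support:
- **That side-lying data are entered in the calculator.** No text says so. The calculator only fails to exclude them.
- **That the calculator uses roll alone.** It takes pitch and roll. The gap is the missing torso input.
- **That nothing ties head roll to supine sleep.** Section 2 does so, loosely.
- **That reductions above 80% are to be expected**, because the 0 or 180 row is Side only and 1 − 5/25 = 80%. Step 8 never schedules that angle, the row is openly labelled Side, and a prior diagnosis of positional apnea does not guarantee a non-supine AHI below 5 on the study night.

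**Conclusion.** The concern holds as a mismatch between a supine-only question and tools that do not keep to it. Nothing beyond one vague sentence limits each angle's AHI, the below-5 determination or the algorithm to supine sleep.

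As an illustration, a 20–50% side-lying share gives a false reduction of 18–46%. The range is 16–50% when non-supine AHI runs from 0 to 4.9. This assumes no head effect, supine AHI 25 and pooling of side-lying with supine time. The share is an assumption, not a forecast.

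The main exposure is the algorithm. The below-5 determination is less exposed, since in a mixed segment it needs mostly side-lying time at supine AHI of 10 or more (with non-supine AHI 2), though less at the mildest baselines. For a pilot of up to 10 participants the point should be corrected, but it does not undermine the study: the recordings allow supine-only results.

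**What to change.** 1. Add to Section 2 or Data Analysis: each angle's AHI, the below-5 determination and the algorithm input use only sensor-confirmed supine sleep. AHI at an angle is supine events at that angle divided by supine sleep hours at that angle.
2. Add that side-lying data are reported separately, which keeps them available for the Section 1 hypothesis.
3. Give each Appendix A row a single torso position, and record its supine sleep minutes.
4. Label the calculator, including its peak AHI input, as applying to supine sleep.

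This costs two sentences, a form edit and a label. The existing head and body sensors record what is needed. The downside is fewer usable minutes at some angles, and so a less precise AHI there.
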